7.3.5 Validity and Reliability

All the clinical trials included in this pooled study have completed the clinical study report and the analysis datasets and variables have been validated by sponsor. In this pooled

analysis, each individual trial will follow its own derivations of the endpoints and variables, which are specified in its own SAP.

7.4 Data Sources

All subject data in the selected clinical trials were recorded on the Clinical Research Form (CRF) unless transmitted to the sponsor electronically. The investigator verified the accurate data entries by signing the CRF. Clinical monitors performed source data verification to confirm that CRF data are accurate. The sponsor data management department performed the edit check outlined in the data management plan on file. The analysis datasets and variables of each individual clinical trials in this pooled analysis have been validated by sponsor. Variables from each individual trial will follow its own derivations specified in its own SAP. All data among sources can be linked based on the unique identifier for each subject. For further details, please see Sections 8.1 and 8.2 of the SAP.

7.5 Study Size

As of 14 July 2019, there are approximately 604 subjects from 9 clinical trials for K monotherapy and 1,213 subjects from 9 clinical trials for Kd. The sample size for the primary analysis described in [Section 7.7.1.1](#) is 564 subjects from 5 clinical trials for K monotherapy and 1,199 subjects from 6 clinical trials for Kd ([Table 1](#)). The sample size for the subsequent sensitivity analysis described in [Section 7.7.2.5](#) is 604 subjects from 9 clinical trials for K monotherapy and 1,213 subjects from 9 clinical trials for Kd ([Table 2](#)).

The sample size is based on the inclusion criteria specified in [Section 7.2.1](#). In this pooled analysis, the primary objective is to describe the benefit-risk profile for each K dosing regimen based on the clinical parameters that are associated with efficacy and safety outcomes. All analyses will be descriptive.

7.6 Data Management

As noted in Section 8.7 of the SAP, programs will be developed and maintained and output will be verified in accordance with current risk-based quality control procedures. Tables, figures, and listings will be produced with validated standard macro programs where standard macros can produce the specified outputs. The production environment for statistical analyses consists of Amgen-supported versions of statistical analysis software; for example, the SAS System version 9.4 or later.

7.6.1 Obtaining Data Files

The Amgen Global Study Operations-Data Management (GSO-DM) department will provide all data to be used in the planned analyses. The data of individual clinical trial were entered in Onyx owned clinical databases and Amgen RAVE database. The data handling and electronic transfer of data are described in the data management plan on file. No linking of data files is necessary. For further details, please see Section 8 of the SAP.

7.6.2 Review and Verification of Data Quality

The database of each individual clinical trial was subject to edit checks outlined in the data management plan. Data inconsistencies and suspicious values were reviewed and resolved before the database was locked for analyses in clinical study report. The analysis datasets and variables in each individual clinical trial had been validated by sponsor. In this pooled study, each individual trial will follow its own derivations of the endpoints and variables, which are specified in its own SAP.

7.7 Data Analysis

7.7.1 Planned Analyses

The planned analysis will be based on the subjects pooled from the clinical trials that meet the eligible criteria outlined above, which is further described in [Table 1](#).

Table 1. Summary of Individual Clinical Trials to Derive Subject Data for Pooled Analysis

Study Number	Study Title	Subject Population	Design	Objectives	Drug Combination/ K Dose Schedule ^a	Eligible Subjects (K regimen: subject #)
20160275	A Randomized, Open-label, Phase 3 Study Comparing Carfilzomib, Dexamethasone, and Daratumumab to Carfilzomib and Dexamethasone for the Treatment of Patients with Relapsed or Refractory Multiple Myeloma (CANDOR)	Relapsed or refractory MM	Phase 3, randomized, active-controlled	Efficacy; safety	Carfilzomib + dexamethasone + daratumumab (Dara) vs carfilzomib + dexamethasone K 20/56 mg/m ² (30 min) Dara 16 mg/kg up to 4 years	Kd: 153 subjects
20140355 (CFZ014)	A Randomized, Open-label, Phase 3 Study in Subjects With Relapsed and Refractory Multiple Myeloma Receiving Carfilzomib in Combination With Dexamethasone, Comparing Once-weekly Versus Twice-weekly Carfilzomib Dosing (A.R.R.O.W.)	Relapsed and refractory MM	Phase 3, randomized	Efficacy; safety	Carfilzomib + dexamethasone K 20/70 mg/m ² QW (30 min) K 20/27 mg/m ² BIW (10 min)	Kd27: 235 subjects

Footnotes defined on last page of the table

Table 1. Summary of Individual Clinical Trials to Derive Subject Data for Pooled Analysis

Study Number	Study Title	Subject Population	Design	Objectives	Drug Combination/ K Dose Schedule ^a	Eligible Subjects (K regimen: subject #)
20140242 (CFZ005)	An Open-label, Single-arm, Phase 3 Study of Carfilzomib in Combination With Dexamethasone in Subjects With Relapsed and Refractory Multiple Myeloma in China	Relapsed and refractory MM; ≥ 2 prior tx	Phase 3, single arm	Efficacy	Carfilzomib + dexamethasone K 20/27 mg/m ² (30 min) dex 20 mg	Kd27: 123 subjects
20140122 (PX-171-002 Part 1 and Part 2)	A Phase 1 Study of the Safety and Pharmacokinetics of Escalating Intravenous Doses of the Proteasome Inhibitor PR-171 in Patients with Hematological Malignancies: Four-week Cycle	MM, NHL, WM, or HD; relapsed or refractory after ≥ 2 prior tx	Phase 1, dose escalation/ expansion	Safety and tolerability; establish MTD; PK	Carfilzomib Part 1: 1.2 to 27 mg/m ² (2 min) Part 2: 20/27 mg/m ² (10 min) up to 12 cycles	K27: 7 subjects Kd27: 3 subjects
20140120 (PX-171-005)	Phase 2 Study of the Safety and Pharmacokinetics of carfilzomib in Subjects with relapsed and Refractory Multiple Myeloma and Varying Degrees of Renal Function	Relapsed and refractory MM; ≥ 2 prior tx; varying degrees of renal function	Phase 2, single arm, parallel cohorts by CrCL grouping	PK; safety and tolerability; PDn; QTc; efficacy	Carfilzomib 15/20/27 mg/m ² (2 to 10 min)	K27: 8 subjects Kd27: 20 subjects

Footnotes defined on last page of the table

Table 1. Summary of Individual Clinical Trials to Derive Subject Data for Pooled Analysis

Study Number	Study Title	Subject Population	Design	Objectives	Drug Combination/ K Dose Schedule ^a	Eligible Subjects (K regimen: subject #)
20140119 (PX-171-004 – Part 1 and Part 2)	An Open-label, Single-arm, Phase 2 Study of Carfilzomib in Patients with Relapsed and Refractory Multiple Myeloma	Relapsed or refractory MM; 1 to 3 prior tx	Phase 2 Part 1: single arm Part 2: 2 dosing cohorts	Safety; efficacy; PK	Carfilzomib Part 1: 20 mg/m ² (10 min) Part 2: 20 or 20/27 mg/m ² (10 min) up to 12 cycles	K27: 78 subjects
20140118 (PX-171-003 – Part 1 (A0) and Part 2 (A1))	An Open-label, Single-arm, Phase 2 Study of Carfilzomib in Patients with Relapsed and Refractory Multiple Myeloma	Relapsed and refractory MM; ≥ 2 prior tx	Phase 2, single arm	Efficacy; safety; PK; PDn	Carfilzomib Part 1: 20 mg/m ² (2 min) Part 2: 20/27 mg/m ² (10 min) up to 12 cycles	K27: 200 subjects
20130402 (CFZ002)	An Open-label, Single Arm, Phase 1 Study of the Pharmacokinetics and Safety of Carfilzomib in Subjects with Advanced malignancies and varying Degrees of Hepatic Impairment	Relapsed or progressive advanced malignancies; ≥ 2 prior tx; varying degrees of hepatic function	Phase 1, comparative PK with 4 cohorts based on liver function	Assess hepatic impairment on AUC	Carfilzomib + dexamethasone K 20/27/56 mg/m ² (30 min) dex 8 mg BIW	K56: 2 subjects

Footnotes defined on last page of the table

Table 1. Summary of Individual Clinical Trials to Derive Subject Data for Pooled Analysis

Study Number	Study Title	Subject Population	Design	Objectives	Drug Combination/ K Dose Schedule ^a	Eligible Subjects (K regimen: subject #)
20130401 (CFZ001)	An Open-label, Single Arm, Phase 1 Study of the Pharmacokinetics and Safety of Carfilzomib in Subjects with Relapsed Multiple Myeloma and End-stage Renal Disease	Relapsed or refractory MM; ≥ 1 prior tx; normal renal function or ESRD on hemodialysis	Phase 1, comparative PK with 2 cohorts based on CrCL	Assess influence of ESRD on AUC	Carfilzomib + dexamethasone K 20/27/56 mg/m ² (30 min) dex 8 mg BIW	K27: 4 subjects K56: 19 subjects Kd56: 3 subjects
20130398 (2011-003)	A Randomized, Open-label, Phase 3 Study of Carfilzomib Plus Dexamethasone Versus Bortezomib Plus Dexamethasone in Patients With Relapsed Multiple Myeloma (ENDEAVOR)	Relapsed MM; 1 to 3 prior tx	Phase 3, randomized, active-control	Efficacy; safety	Carfilzomib + dexamethasone vs bortezomib (V) + dexamethasone K 20/56 mg/m ² (30 min) dex 20 mg V 1.3 mg/m ²	Kd56: 463 subjects
20130396 (PX-171-011)	A Randomized, Open-label, Phase 3 Study of Carfilzomib vs Best Supportive Care in Subjects with Relapsed and Refractory Multiple Myeloma (FOCUS)	Relapsed and refractory MM; ≥ 3 prior tx	Phase 3, randomized, active-control	Efficacy; safety	Carfilzomib vs best supportive care K 20/27 mg/m ² (10 min) Corticosteroid (prednisolone 30 mg or dex 6 mg every other day) Optional CYC 50 mg QD	K27: 157 subjects

Footnotes defined on next page of the table

Table 1. Summary of Individual Clinical Trials to Derive Subject Data for Pooled Analysis

Study Number	Study Title	Subject Population	Design	Objectives	Drug Combination/ K Dose Schedule ^a	Eligible Subjects (K regimen: subject #)
20130393 (PX-171-007)	Phase 1b/2, Multicenter Open-label Study of the Safety and Activity of Carfilzomib in subjects with Relapsed Solids Tumors, Multiple Myeloma, or Lymphoma	Relapsed or refractory MM; ≥ 2 prior tx	Phase 1b/2, dose escalation	Safety and tolerability	Carfilzomib 20/36 to 20/70 mg/m ² (30 min)	K56: 24 subjects Kd56: 8 subjects
					Carfilzomib + dexamethasone K 20/45 or 20/56 mg/m ² (30 min)	
2011-002	Carfilzomib Multiple Myeloma Expanded Access protocol (C-MAP) for Subjects with Relapsed and Refractory Disease (C-MAP)	Relapsed or refractory MM; ≥ 4 prior tx; unable to enroll in another US CFZ study	Phase 2, single arm; expanded access program	Safety	Carfilzomib 20/27 mg/m ² (10 min)	K27: 105 subjects Kd27: 205 subjects

Page 5 of 5

ALL = acute lymphoblastic leukemia; AUC = area under the concentration-time curve; BIW = twice weekly; BTZ = bortezomib; CFZ = carfilzomib; C-MAP = Carfilzomib Multiple Myeloma Expanded Access Protocol; CrCL = creatinine clearance; CYC = cyclophosphamide; Dara = daratumumab; DDI = drug-drug interaction; DEX = dexamethasone; ESRD = end-stage renal disease; HD = Hodgkin's disease; LEN = lenalidomide; MEL = melphalan; Mito = mitoxantrone; MM = multiple myeloma; MTD = maximum tolerated dose; NHL = non-Hodgkin's lymphoma; PDn = pharmacodynamics; PEG = polyethylene glycol; PK = pharmacokinetics; POM = pomalidomide; PRED = prednisone; QD = once daily; QTc = corrected QT interval; QW = once weekly; R3 = dexamethasone, mitoxantrone, PEG-asparaginase, and vincristine; SCLC = small-cell lung cancer; tx = therapy(ies); US = United States; VCR = vincristine; VXLD = vincristine, dexamethasone, PEG-asparaginase, and daunorubicin; WM = Waldenström's macroglobulinemia
 Studies 2011-003 (ENDEAVOR) and 2012-005 (CLARION) are co-sponsored by Amgen and Ono Pharmaceutical Co, Ltd. in Japan and is sponsored solely by Amgen in other participating countries. All other studies are sponsored solely by Amgen.
 All studies were open-label.

^aUnless otherwise noted, carfilzomib was administered in 28-day cycles on days 1, 2, 8, 9, 15, and 16 until progressive disease. Stepped-up dosing was allowed on cycle 1 day 8 for Studies PX-171-009 (ASPIRE), PX-171-011 (FOCUS), 2011-003 (ENDEAVOR), PX-171-007, 2011-002, CFZ001, CFZ002, 20140242 (CFZ005), 20140355 (A.R.R.O.W.), 20160275 (CANDOR); on cycle 2 day 1 for Studies PX-171-002 – Part 2, PX-171-003 – Part 2 (A1), PX-171-004 – Part 2, and PX-171-005. Where applicable, and unless otherwise noted, dexamethasone was administered at 40 mg weekly.

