7.7.1.1 Primary Analysis

In response to the anticipated variations in the sample sizes and data variables collected for these 13 clinical trials, there will be a primary analysis and a subsequent sensitivity analysis to avoid the introduction of extra-variation to the pooled data. The primary analysis will consist of all studies that meet the eligibility criteria with an adequate sample size of at least 20 subjects and at least 80% completeness of data for each variable in [List 1](#) (Table 2). This yields 5 clinical trials for K monotherapy totaling 564 subjects and 6 clinical trials for Kd totaling 1,199 subjects.

Table 2. Clinical Trials for Primary Data Analysis

K27 (540 subjects)	K56 (24 subjects)	Kd27 (583 subjects)	Kd56 (616 subjects)
20140119 (78 subjects)	20130393 (24 subjects)	20140355 (235 subjects)	20160275 (153 subjects)
20140118 (200 subjects)		20140242 (123 subjects)	20130398 (463 subjects)
20130396 (157 subjects)		20140120 (20 subjects)	
2011-002 (105 subjects)		2011-002 (205 subjects)	

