7.7.2.4 Analysis of the Primary, Secondary, and Exploratory Endpoint(s)

For the primary endpoint, the analyses will describe the distribution of each clinical parameter and the distribution of each efficacy/safety outcome by each dosing regimen (K27, Kd27, K56, and Kd56) to yield a summary of the favorable versus unfavorable effects for each dosing regimen.

For the secondary and exploratory endpoints, the outcomes for efficacy will use the well-established endpoints of PFS, an approved surrogate marker of overall survival, and ORR, one of the most commonly used endpoints in myeloma clinical trials. Each individual trial will follow its own definition of PFS and ORR, which was specified in its respective SAP, to derive these pooled data. For analyses of PFS, Kaplan-Meier estimates will be used to estimate the median and other quartiles along with corresponding two-sided 95% confidence intervals. For analyses of ORR, the associated 95% exact binomial confidence interval (Clopper-Pearson method) will be

reported for Kd56 versus Kd27 and Kd27 versus K27. Risk ratio (RR) with the corresponding 95% CIs for Kd56 versus Kd27 and Kd27 versus K27 will be estimated using Cochran-Mantel-Haenszel (CMH) method. To account for potential differences in drug exposure duration, exposure-adjusted incidence rate with the corresponding 95% CI will also be calculated.

Also, for the secondary and exploratory endpoints, outcomes for safety will use endpoints of all fatal events as well as grade 3 or higher and serious adverse events (AEs) of special interest (List 2). Classification of the severity of AEs from each trial will be in accordance with the NCI-CTCAE criteria used during that individual clinical trial, which was also specified in its respective SAP. The number and percentage of subjects experiencing the treatment-emergent adverse event (TEAE) by system organ class/preferred term (SOC/PT) will be summarized for the specified safety outcomes and presented side-by-side for the 4 dosing regimens (K27, K56, Kd27, Kd56) overall for both the primary and sensitivity analyses.

List 2. Adverse Events of Special Interest (in alphabetical order)

- Acute renal failure (SMQN)
- Cardiac events (Sum of events for cardiac failure [SMQN] + ischemic heart disease [SMQN] + torsades des points including QT prolongation [SMQB])
- Cardiac failure (SMQN)
- Hypertension (SMQN)

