7.7.2.5 Sensitivity Analysis

For the primary endpoint, the subsequent sensitivity analysis will consist of all studies that meet the eligibility criteria described above without regard to sample size or completeness of data ([Table 3](#)). This yields 9 clinical trials for K monotherapy totaling 604 subjects and 9 clinical trials for Kd totaling 1,213 subjects.

Table 3. Clinical Trials for Sensitivity Data Analysis

K27 (559 subjects)	K56 (45 subjects)	Kd27 (586 subjects)	Kd56 (627 subjects)
20140122 (7 subjects)	20130402 (2 subjects)	20140355 (235 subjects)	20160275 (153 subjects)
20140120 (8 subjects)	20130401 (19 subjects)	20140242 (123 subjects)	20130398 (463 subjects)
20140119 (78 subjects)	20130393 (24 subjects)	20140122 (3 subjects)	20130393 (8 subjects)
20140118 (200 subjects)		20140120 (20 subjects)	20130401 (3 subjects)
20130396 (157 subjects)		2011-002 (205 subjects)	
20130401 (4 subjects)			
2011-002 (105 subjects)			

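### In the sensitivity set, the K56 acute renal failure percentage can be distorted by renal status at entry, because 19 of its 45 subjects come from a trial with a hemodialysis cohort

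*Protocol*

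**What the plan says.** - **Outcome.** The abstract's objectives table and List 2 in Protocol Section 7.7.2.4 name acute renal failure (SMQN) as a key risk, counted when grade 3 or higher or serious.
- **Summary measure.** Section 7.7.2.4 asks for the number and percentage of subjects with the treatment-emergent event, shown side by side for K27, K56, Kd27 and Kd56, "overall for both the primary and sensitivity analyses". It restricts no outcome to subjects at risk of it.
- **Exclusions.** Section 7.2.1.2 removes only subjects duplicated across regimens.
- **The study.** Table 1 describes study 20130401 as a two-cohort pharmacokinetic comparison in subjects with "normal renal function or ESRD on hemodialysis". Its eligible subjects are given as "K27: 4 subjects K56: 19 subjects Kd56: 3 subjects". The split between the two cohorts is not given.
- **Analysis sets.** Table 3 (sensitivity) includes this study. Table 2 (primary) does not: its 24 K56 subjects all come from study 20130393.
- **Comparisons.** Section 7.7.2.4 states that K27 versus K56 is left out because K56 is too small.

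**The concern.** A percentage of subjects with an event describes risk only if the subjects in the denominator could have the event and the numerator counts new events. Study 20130401 recruited one of its cohorts because of renal failure, so for this outcome its entry criterion and the outcome touch. If all regimens held a similar share of such subjects, the side-by-side table would at least be even. They do not: nearly all subjects from this study are in K56.

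Two things are at stake. The first is the K56 renal figure in the sensitivity table, which could move for a reason unrelated to dose. The second is what the sensitivity analysis can show for K56. This study supplies most of the subjects who are added to the primary set, so a change in the renal percentage between the two sets could simply be the effect of adding it.

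Nothing else in the protocol corrects the figure. K56 enters no propensity-matched comparison. Subgroups by creatinine clearance or chronic kidney disease are optional (Section 7.7.2.5.1) and leave the overall percentage as it is. An exposure-adjusted rate would still count the time of subjects on dialysis.

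**Working it through.** **1. Reproduce Table 3.** The column totals agree with the protocol:
- K56: 2 + 19 + 24 = 45
- K27: 7 + 8 + 78 + 200 + 157 + 4 + 105 = 559
- Kd27: 235 + 123 + 3 + 20 + 205 = 586
- Kd56: 153 + 463 + 8 + 3 = 627

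**2. Share of study 20130401 in each regimen (Tables 1 and 3).**
- K56: 19/45 = 42.2%
- K27: 4/559 = 0.7%
- Kd56: 3/627 = 0.5%
- Kd27: 0/586 = 0%

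From primary to sensitivity set, K56 gains 45 − 24 = 21 subjects, of whom 19 (90%) come from this study.

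**3. Dilution.** Let *e* be the number of the 19 who were on dialysis at entry (not stated, so 0 to 19), and *r* the risk in the other K56 subjects. If dialysis subjects cannot register the event:

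reported risk = r × (45 − e)/45

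With an assumed r of 10%:

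| e | At-risk N | Reported risk | Relative understatement |
|---|---|---|---|
| 0 | 45 | 10.0% | 0% |
| 5 | 40 | 8.9% | 11% |
| 10 | 35 | 7.8% | 22% |
| 15 | 30 | 6.7% | 33% |
| 19 | 26 | 5.8% | 42% |

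The same formula caps the understatement from this study at 0.7% in K27 and 0.5% in Kd56.

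**4. Inflation.** If *c* of the *e* dialysis subjects are nevertheless coded to the SMQ:

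reported risk = [r × (45 − e) + c]/45

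This exceeds r once c > r × e. With r = 10% and e = 10, the reported risk is 7.8% for c = 0, (3.5 + 1)/45 = 10.0% for c = 1, and (3.5 + 2)/45 = 12.2% for c = 2. The sign of the distortion therefore depends on coding, and a couple of coded subjects are enough to reverse it.

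**5. What the tables imply about e.** The study has 4 + 19 + 3 = 26 eligible subjects, of whom 4 + 3 = 7 lie outside K56. Any total above 7 with ESRD must place some in K56. If the cohorts were equal among eligible subjects (13 each, an assumption), at least 13 − 7 = 6 of the 45 K56 subjects (13%) would be on dialysis.

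**6. Precision.** With an assumed 3 events, all in at-risk subjects, the exact 95% intervals are:
- 3/45 = 6.7% (1.4 to 18.3)
- 3/35 = 8.6% (1.8 to 23.1)
- 3/26 = 11.5% (2.4 to 30.2)

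**The case against.** The strongest case against is that this touches one outcome in one regimen of a secondary data set, within a study that is descriptive throughout. The primary K56 set is untouched. The protocol says repeatedly that K56 is too small for a robust comparison with K27. The intervals in step 6 overlap almost entirely, so random error is larger than the likely distortion. Treatment-emergent counting should keep pre-existing ESRD out of the numerator. That a subject on dialysis cannot have acute renal failure is a clinical assumption that the protocol does not make. An all-treated denominator is a common safety convention. Creatinine clearance and chronic kidney disease will be tabulated by regimen, so an unusual renal mix would be seen. The SAP, to which the protocol refers for detail and which was not available here, may define an outcome-specific denominator.

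Most of this stands and limits the point. It does not remove it. Baseline tables show the mix but do not tell a reader what the renal percentage would be without it. Wide intervals do not excuse a shift that could be shown at once. If treatment-emergent counting works as intended, the numerator is protected but the denominator is not. The uncertainty over whether dialysis subjects can register the event is a reason to show both figures. The protocol as written counts every subject.

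A reader might also infer that study 20130401 belongs in the primary set, since its 26 eligible subjects exceed the threshold of 20. Table 2 does not support that: the threshold is applied within each regimen. Study 20140120 enters for Kd27 with 20 subjects but not for K27 with 8, and study 20130393 enters for K56 with 24 but not for Kd56 with 8. The largest regimen group in study 20130401 is 19.

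**Conclusion.** The point holds for the sensitivity set only. The K56 acute renal failure percentage there rests on a denominator of which 42% comes from a trial with a hemodialysis cohort, against less than 1% in any other regimen, and the protocol gives no way to see the effect.

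The size cannot be fixed from the document. If dialysis subjects cannot register the event, the relative understatement lies between 0% and 42%. The upper end needs all 19 to have been on dialysis, in a study that also had a normal-function cohort, so it is a bound and not an estimate. If entry status is coded as an event, the error runs the other way.

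Two stronger readings are not supported. One is that the primary K56 result is affected: the study is not in Table 2. The other is that the plan would bias a K27 versus K56 comparison: none is planned, and the protocol rules it out for lack of subjects. What remains is a figure in a side-by-side table that cannot be interpreted without knowing how many subjects were on dialysis.

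**What to change.** In Sections 7.7.2.4 and 7.7.2.5:

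- State the number of subjects with ESRD or on dialysis at baseline, by regimen.
- For acute renal failure in the sensitivity set, keep the all-subject percentage. Beside it, report the percentage with these subjects removed from both numerator and denominator, in all four regimens, with the at-risk N shown.
- Leave these subjects in for every other outcome.

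The cost is one baseline flag, one extra table row and a footnote. List 1 has no dialysis item, so it needs to be checked that each pooled trial's data can supply the flag. The K56 denominator in the added row will be smaller, between 26 and 45 if only study 20130401 contributes such subjects, and its interval correspondingly wider. The all-treated convention is kept, and no primary result changes.
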